Statistical Methods	
Analysis Populations The transplanted recipient population will consist of all recipients who are transplanted. The Per-Protocol (PP) population will consist of all recipients who are transplanted without a major protocol violation. The primary analyses of all effectiveness and safety endpoints will be based on the Per Protocol population. Supportive analyses for all endpoints will be provided for the transplanted recipient population
 
Effectiveness There are two co-primary hypotheses for this trial.
 
 • Co-Primary Hypothesis #1 The first co-primary hypothesis is that the proportion of transplanted recipients of lungs preserved using the OCSTM Lung System surviving at Day 30 and at initial hospital discharge post-transplantation (whichever occurs later) is greater than a performance goal based on the corresponding proportion of patients in the Per-Protocol population of the Control arm of the INSPIRE trial (0.939) with a margin of 0.12 (12%). The formal statistical hypothesis test is as follows: $H_0: \pi_{OCS\ Lung} \leq 0.819$ $H_1: \pi_{OCS\ Lung} > 0.819$ where $\pi_{OCS\ Lung}$ is the proportion of transplanted recipients alive Day 30 and at initial hospital discharge. This co-primary effectiveness endpoint will be summarized using a count and percentage with an exact 95% confidence interval for the percentage based on the binomial distribution. A one-sided exact binomial test at the 0.025 significance level will be performed to test the null hypothesis H_0. • Co-Primary Hypothesis #2 The second co-primary hypothesis is that the Utilization Rate (defined above) is greater than a performance goal of 0.54 (54%), which is based on the utilization rate reported for XVIVO in the NOVEL Trial (FDA Executive Summary for XVIVO, p.53). The formal statistical hypothesis test is as follows: $H_0: \pi_{OCS\ Lung} \leq 0.54$ $H_1: \pi_{OCS\ Lung} > 0.54$ where $\pi_{OCS\ Lung}$ is the observed utilization rate in the EXPAND trial. This co-primary effectiveness endpoint will be summarized using a count and percentage with an exact 95% confidence interval for the true percentage based on the binomial distribution. A one-sided exact binomial test at the 0.025 significance level will be performed to test the null hypothesis, H_0. 
Secondary Effectiveness Endpoints The secondary effectiveness endpoints will be summarized using counts and percentages and an exact 95% confidence interval for the true percentage based on the binomial distribution.
 
Safety Safety will be analyzed principally by examination of the frequency of adverse events. In particular, the number of lung graft-related serious adverse events (SAEs) up to the 30-day follow-up or until initial hospital admission (if longer than 30 days) after transplantation per subject will be analyzed. This endpoint is defined to consist of the following adverse events (at most one per type), if they are serious adverse events (as defined in Appendix 3):
 
 • Acute rejection

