6.3. Subject Identification

All patients on the transplant waiting list, or in the process of listing on the transplant waiting list, who are being approached by trial investigators for consent for this trial will be identified in a “screening log” that is maintained by the trial coordinator. Those patients who initially appear eligible for the trial will have the trial thoroughly explained to them, be invited to participate, and will be asked to sign an informed consent for participation in the trial prior to treatment. Only when a final decision is made that donor lungs have met the transplantability criteria on the OCSTM Lung System, the recipient will be assigned a subject identification number. Consented recipients who were transplanted using standard ideal donor lungs outside of the study, or who were transplanted with lungs preserved using cold storage preservation outside of the study, will be considered withdrawn from the EXPAND II Study. Figure 2 below is a flow diagram of donor lung and potential transplant recipients screening and enrollment process for the EXPAND II Trial.

Figure 2: OCSTM Lung EXPAND II Trial Donor Lungs and Recipients Screening and Enrollment Flowchart

A consented potential recipient will be considered withdrawn from the EXPAND II Trial under the following conditions:

- The patient was transplanted using standard donor lungs; or
- The patient was transplanted using cold storage for preservation of the donor lungs.

Potential donor lungs will be considered as a dry run/ineligible under the following conditions:

- The clinical retrieval team deemed the lungs not suitable for clinical transplantation due to pathology or lung conditions;
- Donor lungs did not meet eligibility criteria for the EXPAND II Trial.

To clarify, no clinical outcomes data will be collected on withdrawn recipients or dry run/ineligible donor lungs as defined above.

A subject will be considered a screen failure for EXPAND II under the following conditions:

- The recipient fails to meet inclusion/exclusion criteria on the day of the potential transplant when eligible donor lungs are accepted for transplantation after OCSTTM Lung System preservation and assessment.
- Transplant center or OPO logistical reasons prevent transplantation of donor lungs preserved using the OCSTTM Lung System:

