 - Date and time of cross clamp of donor pulmonary artery (PA)
 - For DCD donors, dates and times will be collected for the following:
 - Withdrawal of support
 - Announcement of cardiac arrest
 - Cross clamp of the Pulmonary Artery
 - 1st and 2nd transplanted lung cross-clamp times
 - 1st and 2nd transplanted lung ischemic times
 - Use of Cardiopulmonary Bypass CPB (if applicable) and length of time on CPB will be collected.
- **OCSTTM Details (lung instrumentation details):**
 - Donor lungs instrumentation on the OCSTTM Lung System date and time
 - Perfusate volume and ABO type of the pRBCs units used to prime the OCSTTM.

- **OCSTTM Measurements:** The following OCSTTM Lung System perfusion and ventilation parameters as well as lung oxygenation capacity will be recorded:
 - Final PaO₂/FiO₂ ratio on OCSTTM (at initial and final Continuous Monitoring Mode at the recipient's hospital after the retrieval)
 - Mean Pulmonary Artery Pressure (PAP) trend
 - Pulmonary Vascular Resistance (PVR) trend
 - Peak Airway Pressure (PAWP) trend.

6.5. **Donor Lung Acceptance for Transplantation After OCSTTM Lung Assessment**

- All donor lungs preserved on OCSTTM Lung System must meet at least one of the two following standard clinical criteria for transplantation at final assessment on OCSTTM Lung System¹¹:
 - Final OCSTTM Lung System PaO₂/FiO₂ ratio of ≥ 300 mmHg at the end of OCSTTM perfusion
 - Stability of PAP, PVR, & PAWP trends defined to be stable or <20% worsening (i.e., increase) of each of these parameters from beginning (at initial assessment in Continuous Monitoring Mode) to end of OCSTTM perfusion (at final assessment in Continuous Monitoring mode)

AND the following criteria must be met in addition to the above:

- Lungs are clinically acceptable by the Site Principal Investigator based on their clinical judgment.
- Any decision to turn down lungs after the lungs have been retrieved, preserved and assessed on OCSTTM Lung System should be done with notification to the Site Principal Investigator and document the clinical reason for turning down the donor lung for transplantation.

7. **TRANSPLANT, IMMEDIATE POST-OPERATIVE AND LONG-TERM FOLLOW-UP**

7.1. **Transplant Details**

- Information concerning the transplant procedure, such as: name of the surgeon, organ recipient unique post-transplant patient identifier, date of transplant, skin incision time, the use of and duration on cardiopulmonary bypass, time of completion of procedure/ OR discharge time.

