9.7. Sample Size Determination

The sample size for this trial was determined based on providing adequate statistical power for hypothesis testing of the two co-primary effectiveness endpoints. All sample size calculations were performed using PROC POWER in SAS.

For the first co-primary endpoint, the calculations assumed a one-sided exact binomial test, an alpha level of 0.025, a control-based rate of 0.939 with a margin of 0.12 (to derive the performance goal of 0.819), a true survival rate for OCST™ of 0.939, and desired power of 90%. Based on these specifications, the required sample size was determined to be 84 transplanted recipients.

For the second co-primary endpoint, the calculations assumed a one-sided exact binomial test, an alpha level of 0.025, a performance goal of 0.54, a utilization rate of 72% for OCST™, and desired 90% power. Based on these specifications, the required sample size was determined to be 84 transplanted recipients

In order to ensure that a sufficient number of subjects are evaluable in the per-protocol population of the trial, 90 transplanted recipients in the study is expected to provide adequate power to evaluate the two co-primary effectiveness objectives given the assumptions described.

Due to multiple primary endpoints, the Hochberg Method⁵⁵ will be used to control familywise error. The p-values for each of the co-primary endpoints will be ordered from highest to lowest. If the highest p-value is less than 0.025 then both endpoints achieve statistical significance and the null hypothesis of each co-primary endpoint can be rejected. If not, then the lower of the two p-values will be assessed against a significance level of 0.0125. If the adjusted significance level of 0.0125 is applied to any of the co-primary endpoints, the power of that analysis will be greater than 85%. Therefore, the study will be considered successful in either of the two scenarios described above.

With regard to the primary safety endpoint, the pre-specified safety margin of 0.7 events per patient, the estimated mean of 0.29 events per patient (with an estimated standard deviation of 2.0), a one-sided alpha of 0.025, and the sample size of 90 transplanted recipients results in power greater than 90% when considering a one-sample t-test on the mean.

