14.5. Data Safety Monitoring Board and Stopping Rules

An independent Data Safety Monitoring Board (DSMB) will be established by the Sponsor to periodically assess the progress of the trial, the safety data and the primary efficacy and safety endpoints. The DSMB will make recommendations to the Sponsor regarding continuation, modification or termination of the clinical trial. The DSMB will review all data submitted to them by the Sponsor and may request additional information to assist in their decision process. They will attend scheduled meetings and issue written minutes of their meetings; furthermore, the appointed Chair will be responsible for issuing final written recommendations.

The independent stopping rules below will be used in the study (violation of either rule warrants discontinuation of the study).

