### **3.4. Determination of Sample Size**

The sample size for this trial was determined based on providing adequate statistical power for hypothesis testing of the two co-primary effectiveness endpoints. All sample size calculations were performed using PROC POWER in SAS.

For the first co-primary endpoint, the calculations assumed a one-sided exact binomial test, an alpha level of 0.025, a control-based rate of 0.939 with a margin of 0.12 (to derive the performance goal of 0.819), a true survival rate for OCS™ of 0.939, and desired power of 90%. Based on these specifications, the required sample size was determined to be 84 transplanted recipients.

For the second co-primary endpoint, the calculations assumed a one-sided exact binomial test, an alpha level of 0.025, a performance goal of 0.54, a utilization rate of 72% for OCS™, and desired 90% power. Based on these specifications, the required sample size was determined to be 84 transplanted recipients

In order to ensure that a sufficient number of subjects are evaluable in the per-protocol population of the trial, 90 transplanted recipients in the study are expected to provide adequate power to evaluate the two co-primary effectiveness objectives given the assumptions described.

Due to multiple primary endpoints, the Hochberg Method will be used to control familywise error. The p-values for each of the co-primary endpoints will be ordered from highest to lowest. If the highest p-value is less than 0.025 then both endpoints achieve statistical significance and the null hypothesis of each co-primary endpoint can be rejected. If not, then the lower of the two p-values will be assessed against a significance level of 0.0125. If the adjusted significance level of 0.0125 is applied to any of the co-primary endpoints, the power of that analysis will be greater than 85%. Therefore, the study will be considered successful in either of the two scenarios described above.

With regard to the primary safety endpoint, the pre-specified safety margin of 0.7 events per patient, the estimated mean of 0.29 events per patient (with an estimated standard deviation of 2.0), a one-sided alpha of 0.025, and the sample size of 90 transplanted recipients results in power greater than 90% when considering a one-sample t-test on the mean.

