### **3.5. Changes to the Protocol-Specified Analyses**

Not applicable.

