#### **5.5. Multiple Comparisons / Multiplicity**

No adjustments for multiple comparisons/multiplicity will be made.

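### SAP 5.5 rules out any multiplicity adjustment while SAP 3.4, Protocol 9.7 and the synopsis require Hochberg, so which co-primary null is rejected can depend on the section followed

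*SAP*

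**What the plan says.** SAP 3.4 orders the two co-primary p-values. If the larger is below 0.025, both nulls are rejected. Protocol 9.7 gives the next step in the same words as the SAP and the synopsis: "If not, then the lower of the two p-values will be assessed against a significance level of 0.0125". All three then add: "Therefore, the study will be considered successful in either of the two scenarios described above".

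SAP 5.5, the section headed for multiplicity, says in full: "No adjustments for multiple comparisons/multiplicity will be made". SAP 3.5, headed "Changes to the Protocol-Specified Analyses", is answered as not applicable, so the SAP declares no departure from the protocol's Hochberg rule.

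The sections that define the tests (SAP 12.1 and 12.2, Protocol 9.3.1 and 9.3.2, and the synopsis under Statistical Methods) each state: "A one-sided exact binomial test at the 0.025 significance level will be performed to test the null hypothesis". None mentions Hochberg or 0.0125.

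**The concern.** An analyst who works from SAP 5.5 and SAP 12 tests each endpoint on its own at 0.025. An analyst who works from SAP 3.4 may reject a lone endpoint only at 0.0125. Both would be following the approved SAP, and they could report different primary results from the same data. Whoever chooses between the sections after seeing the p-values would be choosing the result.

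A second matter is the success sentence. The 0.0125 step is reached only when at least one endpoint has missed 0.025, so passing there means passing on one endpoint. Nothing requires that endpoint to be survival. The study could be called successful on utilization, which contains no recipient outcome, after survival missed a goal already set 12 points below the 93.9% reference rate.

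**Working it through.** **Inputs.** Survival goal 0.819 and planning rate 0.939; utilization goal 0.54 and planning rate 0.72; one-sided exact binomial tests; 84 required and 90 planned recipients (SAP 3.4). Mortality stopping rule: stop if the exact 97.5% lower bound exceeds 0.10, applied from 20 patients (Protocol 14.5.1 text).

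**1. The plan's own figures.** With x successes in n, p = P(Bin(n, goal) ≥ x). The cut-off is the smallest x with p ≤ α, and power is the same tail at the planning rate.
- At n = 84 and α = 0.025, survival needs 76 (power 93.0%) and utilization needs 55 (92.5%). Power stays at or above 90% from n = 84 for both, so the stated 84 reproduces.
- At α = 0.0125, power is 90.2% and 89.2% at n = 90, so the stated figure of more than 85% holds at the planned size. At n = 84 it is 86.0% and 83.4%.

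**2. A pair of results that separates the sections.** Take p = 0.02 and p = 0.30.
- SAP 5.5 with SAP 12: 0.02 < 0.025, so one null is rejected.
- Hochberg: 0.30 is not below 0.025, and 0.02 is not below 0.0125, so none is rejected.

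**3. Survival cut-offs (number alive).**

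| n | at 0.025 | at 0.0125 |
|---|---|---|
| 84 | 76 (p = 0.0226) | 77 (p = 0.0097) |
| 85 | 77 | 78 |
| 86 | 78 | 79 |
| 87 | 79 | 80 |
| 88 | 80 | 81 |
| 89 | 81 | 82 |
| 90 | 82 (p = 0.0116) | 82 (p = 0.0116) |

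At n = 90, 81 alive gives p = 0.0255, which misses both levels. The primary analysis is per-protocol, and the increase from 84 to 90 exists to allow for exclusions, so 84 to 89 is within the range that the plan itself expects.

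**4. Utilization.** Assume 90 accepted lungs out of N instrumented, with p = P(Bin(N, 0.54) ≥ 90):
- N = 141: 0.0115; 142: 0.0149; 143: 0.0191; 144: 0.0243; 145: 0.0304.

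The level therefore matters only at N = 142 to 144. At a true rate of 72%, P(N ≤ 144) − P(N ≤ 141) = 0.9949 − 0.9864 = 0.0085.

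**5. How often the contradiction would bite.** It changes a decision only if the other endpoint also misses at 0.025. At the planning rates:
- Survival at n = 84: (0.930 − 0.860) × P(utilization misses). The second factor is 1 − 0.995 = 0.005 with 90 accepted lungs, or 1 − 0.925 = 0.075 with 84 lungs. The product is 0.0004 to 0.005.
- Utilization with survival at n = 90: 0.0085 × (1 − 0.902) = 0.0008.

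If utilization truly fails, the survival figure approaches 0.070.

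**6. Success on utilization alone.** Apply the text stopping rule after each patient from n = 20. It triggers at 6 deaths in 20, 8 in 30 and 16 in 90, while the survival goal needs at most 8 deaths in 90. Multiply P(complete and miss survival) by P(utilization passes 0.0125) = 0.9864:

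| True survival | Stopped | Completes, misses goal | Success on utilization alone |
|---|---|---|---|
| 0.819 | 0.715 | 0.273 | 0.27 |
| 0.85 | 0.436 | 0.501 | 0.49 |
| 0.939 | 0.004 | 0.0945 | 0.09 |

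Fixing the denominator at 90 or 125 (= 90/0.72) lungs gives 24–26%, 45–49% and 8–9%.

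**7. Price of requiring both endpoints at 0.025,** at the planning rates and without stopping:
- 90 recipients and 90 lungs: 0.902 × 0.928 = 0.837.
- 90 recipients and 125 lungs: 0.902 × 0.987 = 0.891.
- 90 accepted lungs: 0.902 × 0.995 = 0.897.

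Under the written rule, success has probability 98.9% (90 lungs) or 99.7% (125 lungs).

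**The case against.** SAP 5.5 may have been meant for everything except the co-primary pair, since SAP 3.4 already deals with that. But it carries no such limit, and the secondary endpoints are only summarised with confidence intervals, so it has little else to govern.

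The silence of the test sections is weaker evidence, because 0.025 is also Hochberg's first step. That stands: these are omissions, and only SAP 5.5 truly conflicts. Read alone, though, they still reject a lone endpoint at p = 0.02.

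The practical effect is small at the planning assumptions, as step 5 shows. That also stands. It limits the size of the problem but does not settle which rule governs.

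A reader might infer that the plan lets familywise error rise to nearly 5% (1 − 0.975² = 0.0494). The documents do not support this. It pairs SAP 5.5 with a success sentence that appears only inside the Hochberg paragraph. Hochberg as written controls the error.

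A reader might also infer that success on one endpoint is itself an error. It is not: it is prespecified and stated identically in three places, and no passage requires both endpoints or ranks survival first. Survival would still be tested and reported with its interval, so a miss would be visible. There is also a separate safeguard, since under Protocol 14.5 "violation of either rule warrants discontinuation of the study". That safeguard is partial: 9 to 15 deaths among 90 miss the goal without triggering the mortality rule at that point.

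**Conclusion.** The contradiction is real and should be corrected before analysis. SAP 5.5 cannot be followed together with SAP 3.4, Protocol 9.7 and the synopsis, and the test sections do not say which rule governs. At exactly 90 per-protocol recipients the survival decision is unaffected. At 84 to 89 it can turn on one survivor, and with 90 accepted lungs utilization can turn on the section at 142 to 144 instrumented lungs. At the planning rates the chance that a decision changes is about 0.5% or less; the case rests on the text being wrong as written and cheap to correct.

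The success rule is a secondary point for the sponsor to justify or change. With 81 of 90 alive, survival misses its goal and the study may still be called successful. This happens about 27% of the time at true survival 81.9%, 49% at 85% and 9% at 93.9%.

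These figures assume independent endpoints, 72% utilization, outcomes known at once, all 90 recipients per-protocol, exactly 90 accepted lungs, and no success for a stopped study. Accepted lungs could exceed 90, because Protocol 6.3 describes acceptable lungs left untransplanted for logistical reasons; the 141 and 142–144 cut-offs would then move. Other stops by the monitoring board are not modelled and would lower the percentages.

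**What to change.** Replace SAP 5.5 with the Hochberg rule of SAP 3.4 and Protocol 9.7. Refer to the 0.0125 step in SAP 12.1 and 12.2, Protocol 9.3.1 and 9.3.2, and the synopsis under Statistical Methods. State that when only one null is rejected, the claim is limited to that endpoint and the report says that the other goal was not met. This changes wording only: no added patients and no loss of power against the Hochberg plan.

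On the success rule, the sponsor should either give its reason for accepting one endpoint or require both at one-sided 0.025. Requiring both needs no alpha adjustment, so SAP 5.5 could stand as it is and the Hochberg text would be removed. It costs the sponsor success on one endpoint alone: at the planning assumptions the chance of declared success falls from about 99% to about 84–90%, depending on the number of instrumented lungs. If this option is taken, joint power should be stated with its assumed lung denominator.

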### **3.5. Changes to the Protocol-Specified Analyses**

Not applicable.

## 4. EFFECTIVENESS AND SAFETY ENDPOINTS

### 4.1. Primary Effectiveness Endpoint

The study will evaluate two co-primary effectiveness endpoints:

- Patient survival at both 30 days and at initial hospital discharge post-transplantation, whichever occurs later. The basis for this endpoint is the control arm of the INSPIRE trial with a 12% margin.
- Utilization Rate, defined as the number of donated lungs instrumented on OCS™ that meet inclusion/exclusion criteria for the trial and acceptance criteria for transplantation after OCS™ Lung assessment divided by the total eligible donor lungs instrumented on the OCS™ Lung System. The basis for this endpoint is the utilization rate reported for XVIVO in the NOVEL Trial.

Survival at initial hospital discharge post-transplantation is considered to be survival during the initial hospital admission for the transplant procedure through the date of discharge, if it is longer than 30 days.

### 4.2. Secondary Effectiveness Endpoints

The study will evaluate the following secondary effectiveness endpoints:

- Incidence of Primary Graft Dysfunction (PGD) Grade 3 at T72 hours
- Incidence of PGD Grade 3 within the initial 72 hours post-transplantation
- Incidence of Primary Graft Dysfunction (PGD) Grades 2 or 3 at T72 hours
- Incidence of PGD Grades 2 or 3 within the initial 72 hours post-transplantation.

